10.4 Interim analysis and criteria for the premature termination of the trial

The trial will be terminated if there is an unacceptable number of SUSARs or SARs. Any interim data analysis will be performed at the request of the DMC.

10.5 Procedure to account for missing or spurious data

All attempts will be made to avoid and to recover any missing data. In the event of missing data being unrecoverable, a repeat sample may be taken in the case of a blood test. If this is

not possible (e.g. due to interventions being commenced), the participant will be excluded from the trial. Any unused or spurious data will be recorded in the CRF in the section for additional information.

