4 TRIAL DESIGN

This study will be a single centre, open labelled, randomised controlled trial comparing the effect of postoperative oral ferric maltol (intervention group) to standard care (control group), in patients with colorectal adenocarcinoma who have received pre-operative intravenous iron for anaemia. Each patient will be expected to participate for a period of 10 to 20 weeks, depending on the time between their diagnosis and the planned operation date. The participant will be recruited after the cancer MDT meeting confirming the diagnosis of colorectal adenocarcinoma and the ensuring that the patient is suitable for operative management. All study procedures will be undertaken at the time of existing hospital appointments where possible.

Recruitment will take place following the explanation of the cancer diagnosis by the clinical team. The patients will be asked by a member of the clinical or research team to state whether they consent to being approached by the research team for further information regarding the study. If they agree, a face-to-face conversation or a phone call to the patient will be arranged to discuss the research. A letter of invitation to participate in the trial (accompanied by a patient information leaflet) will then be given or posted to the patients. The patient will be given adequate time to consider participation in the study and they will be given the opportunity to ask any questions they may have. Patients who are eligible will then be invited to consent to the study.

After consenting to participate baseline data including demographics, past medical history and existing medications will be noted. Patients will be asked to complete the 3 quality of life questionnaires and they will have their blood taken including a full blood count, haematinics

(including iron, ferritin, transferrin and transferrin saturation) urea and electrolytes, liver function tests and erythropoietin. If the patients have consented to the optional sample sub-study, the patients may be asked to give other samples of faeces, urine, saliva or sweat. Following this visit the patient will receive their preoperative intravenous iron infusion as is standard care. If they are taking any existing oral iron supplementation they will be asked to stop this treatment prior to receiving their preoperative intravenous iron. Once the surgical procedure has been performed, tissue samples from the resected bowel may be obtained for analysis.

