The participant is next reviewed when they are admitted on the morning of the operation.

Blood tests and the quality of life questionnaires will be repeated.

Preoperatively patients will undergo randomisation to one of the two study arms. After operation the participants haemoglobin will be checked on day 2 of their recovery. If, at this point, postoperative anaemia is confirmed they will enter into their study arm. The intervention group will commence a course of oral ferric maltol provided oral intake has recommenced and the control group will receive standard care. All patients will have blood tests checked again at day 3 and day 5 postoperatively if they remain as an inpatient. If they are found to be anaemic on either of these two blood tests they will, at this stage, enter their allocated treatment pathway. If a patient shows no evidence of anaemia on either day 2, 3 or 5 blood tests they will be withdrawn from the study. If the patients have consented to the optional sample sub-study, the patients may be asked to give other samples of faeces, urine, saliva or sweat at days 2, 3 or 5 along with the blood tests. Patients will continue treatment according to their randomisation allocation until 12 weeks after the operation, at which point the patient attends a routine surgical outpatient follow-up clinic. During the outpatient visit the participants will undergo their final blood and optional sample sub-study testing (if consented) as well as questionnaire completion.

The participants may only be required to attend the hospital for one extra visit to consent and where possible this will be arranged to coincide with existing appointments. The study is designed such that all other procedures are carried out when the participant attends for their routine visits as per the normal clinical pathway.

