7.8 Withdrawal criteria

There will be intention-to-treat analyses carried out. Analysis of all participants who have been randomised will be undertaken regardless of withdrawal. The reason for withdrawal will

be recorded in the CRF. Each participant has the right to withdraw study at any time. A participant will be withdrawn from the study if any of the following occurs:

- Absence of anaemia on postoperative days 2, 3 and 5.
- Pregnancy
- Ineligibility (either arising during the study or retrospective having been inadvertently overlooked at screening)
- Significant protocol deviation as defined by the CI
- An adverse event which requires discontinuation of the study medication or results in inability to continue to comply with study procedures
- Disease progression which requires discontinuation of the study medication or results in inability to continue to comply with study procedures
- Patients who do not undergo an operation as a result of a change in fitness for surgery will be excluded.
- Consent withdrawn.
- Lost to follow up

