8.8 Assessment of compliance with treatment

Participants will self-administer the oral ferric maltose tablets. Patients will be asked to declare their compliance with the study drug during the final follow up study visit. If there is a high level of non-compliance (<70%), the patient will be included in the trial under the intention-to-treat-analysis. The reasons for non-compliance will be documented in the CRF.

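### Section 10.5 can remove a randomised participant over one missing blood result, against the all-randomised analysis in 7.8, and 7.8 withdraws those who must stop ferric maltol with no 8–12 week follow-up stated

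*Combined protocol and SAP*

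**What the plan says.** **Missing data.** Section 10.5 asks for missing data to be recovered and allows a blood test to be repeated. If a repeat is "not possible (e.g. due to interventions being commenced), the participant will be excluded from the trial". It names no visit, no analyte and no point relative to randomisation.

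**Analysis set.** Section 7.8 adopts intention to treat: "Analysis of all participants who have been randomised will be undertaken regardless of withdrawal". Section 8.8 says of a participant with compliance below 70% that "the patient will be included in the trial under the intention-to-treat-analysis".

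**Withdrawal.** The list in 7.8 withdraws participants from the study, not only from treatment. Its reasons include "Absence of anaemia on postoperative days 2, 3 and 5" and "An adverse event which requires discontinuation of the study medication or results in inability to continue to comply with study procedures", with a parallel item for disease progression. One item in the list is worded as an exclusion: "Patients who do not undergo an operation as a result of a change in fitness for surgery will be excluded".

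**After stopping.** Section 9.2 gives participants who come off treatment for an adverse event a closing assessment, with no date or content. Appendix 1 lists a withdrawal checklist without its content. Section 8.5 deals separately with temporary interruption.

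**Timing of randomisation.** Section 4 states "Preoperatively patients will undergo randomisation to one of the two study arms". Appendix 1 places randomisation at the day-of-surgery visit. Section 7.7 places it after the operation.

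**The concern.** A rule that removes people because a result is missing sits badly beside a promise to analyse everyone randomised. Here it also acts on the quantities the trial exists to measure. Section 10.3.2 lists withdrawal, retention and outcome completion among the primary feasibility measures and gives no denominator for any of them. A participant removed under 10.5 either leaves the denominator, which raises apparent completion, or counts as not retained because of a data-handling rule.

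The medication-stop rule raises a second problem. Controls receive no study medication, so that trigger can remove participants from the ferric maltol arm only. Hospital records (11.1) may still supply complications, length of stay and transfusions. They cannot supply questionnaires or blood tests that were never taken. The 8–12 week haemoglobin and quality-of-life summaries, which section 3.3.1 intends to use in planning the definitive trial, could then be depleted in one arm.

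**Working it through.** The plan has no figure to reproduce: section 10.1 performs no sample size calculation, and 20 per arm × 2 = 40 agrees with the stated total. The check is a comparison of the text, followed by illustrations in which the counts and rates are assumptions unless a source is given.

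**1. Which draws can 10.5 reach after randomisation?**

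| Draw | Relative to randomisation | Relative to treatment |
|---|---|---|
| Baseline | Before, in every version | Before intravenous iron ("Following this visit the patient will receive their preoperative intravenous iron infusion as is standard care") |
| Day of surgery | Depends on which section is followed | Before ferric maltol |
| Day 2 | After, in every version | Before ferric maltol |
| Days 3 and 5 | After | Before or after ferric maltol starts |
| 8–12 weeks | After | After |

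A missed baseline draw raises no intention-to-treat conflict. The day 2 draw does, even under the rule's own example of treatment having begun: haemoglobin may be available, so ferric maltol starts, while ferritin or erythropoietin from the same draw is missing and can no longer be repeated before treatment.

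**2. Two readings for a randomised participant.** If exclusion means omission from analysis, 10.5 contradicts 7.8. If it means withdrawal with analysis retained, the wording contradiction goes, but one missing result ends follow-up and later outcomes are lost.

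**3. Effect on completion** (Clopper–Pearson 95% CIs; N = 40 from 10.1).

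- 4 of 40 affected: 36/40 = 90% (76–97%), against 36/36 = 100% (90–100%) if they leave the denominator.
- 2 of 40 affected: 38/40 = 95% (83–99%), against 38/38 = 100% (91–100%).
- Two rules together: section 1 gives up to 90% anaemic postoperatively without intervention. Taking the complement, 40 × 0.10 = 4 are withdrawn for no anaemia. If 4 of the other 36 have an unrecoverable result, completion is 32/40 = 80% (64–91%) of all randomised, 32/36 = 89% (74–97%) of those entering the pathway, or 32/32 = 100% (89–100%) if the 10.5 exclusions are dropped as well.

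**4. How many could 10.5 reach?** Let q be the probability that a draw is missing, unrecoverable and unrepeatable, independent across n draws. The proportion reached is 1 − (1 − q)^n, multiplied by 40 for the expected number. The baseline draw is not counted.

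| Draws covered | n | q = 2% | q = 5% | q = 10% |
|---|---|---|---|---|
| Day 2 only | 1 | 2.0% (0.8) | 5.0% (2.0) | 10.0% (4.0) |
| Day of surgery and day 2, if randomised before both | 2 | 4.0% (1.6) | 9.8% (3.9) | 19.0% (7.6) |
| Days 2, 3 and 8–12 weeks | 3 | 5.9% (2.4) | 14.3% (5.7) | 27.1% (10.8) |
| Same plus day 5 (inpatients only) | 4 | 7.8% (3.1) | 18.5% (7.4) | 34.4% (13.8) |

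Section 10.1 rests on 30 or more patients. Solving 40 × (1 − q)^n = 30 gives q = 1 − 0.75^(1/4) = 6.9% for four draws and 1 − 0.75^(1/3) = 9.1% for three.

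**5. Medication-stop rule.** With an assumed 10–20% of the ferric maltol arm having to stop, 20 × 0.90 = 18 to 20 × 0.80 = 16 remain for the 8–12 week outcomes. This trigger causes no matching loss among controls. The other limb, inability to comply with procedures, can act in both arms.

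**The case against.** **The conflict depends on one reading.** Section 7.8 itself describes one of its withdrawal reasons as an exclusion, so 10.5 may be just another withdrawal that is still analysed. That is a fair reading. It removes the contradiction in wording but not the loss of data after removal.

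**The authors probably meant pre-treatment samples.** The example in 10.5 suggests so. If day 2 haemoglobin itself is missing, ferric maltol has not started and the day 3 draw is available. This narrows the day 2 case to partial results, but the rule does not state the restriction, and a pre-treatment draw can still follow randomisation.

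**The denominator is implied.** All randomised is the natural choice under 7.8. That is reasonable, but 10.3.2 does not say it, and 10.5 points the other way.

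**The multi-draw figures are generous.** Non-attenders at 8–12 weeks are already lost to follow-up under 7.8, participants without anaemia leave earlier, and misses cluster within patients. This stands: the three- and four-draw rows are outer bounds, and ordinary miss rates would overstate q because the rule also requires that no repeat is possible. The 10% without anaemia likewise comes from an upper-limit figure for untreated patients.

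**Timing and stopping are partly covered.** Section 4 and Appendix 1 are compatible, and only 7.7 differs. Section 9.2 does assess those stopping for an adverse event. Both are correct, but that assessment is undated, and stopping for progression is not addressed.

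**Conclusion.** The concern holds and should be fixed. As written, 10.5 can remove a randomised participant over a single blood result, and 7.8 turns a required stop of study medication into departure from the study. Both distort primary feasibility measures. That the rules conflict, or end follow-up needlessly, is read directly from the text and needs no assumption.

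The size does rest on assumptions. With 4 of 40 affected, the reading of 10.5 alone moves completion from 90% to 100%; with 2 of 40, from 95% to 100%. The documents give no rate for missing results or for stopping treatment, so neither the actual size nor the direction of the effect on haemoglobin and quality of life can be determined. Because 3.3.1 sets no feasibility criteria and the analysis is descriptive, no pre-set decision is overturned. The damage is to the estimates that will be used to plan the definitive trial.

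**What to change.** - **Section 10.5:** replace exclusion of randomised participants. Keep them in follow-up and in their allocated arm, treat the result as missing for that outcome only, and report the number missing by arm. State that exclusion for a missed draw can apply only before randomisation.
- **Section 4, section 7.7 and Appendix 1:** reconcile the time of randomisation, so that it is clear on which side the day-of-surgery draw falls.
- **Section 10.3.2:** report retention and completion with all randomised as denominator, and also among those who entered the treatment pathway. Show separately by arm those withdrawn by rule for absence of anaemia.
- **Sections 7.8 and 9.2:** separate stopping study medication from leaving the study. Invite those who stop to the 8–12 week blood tests and questionnaires unless they withdraw consent. Report treatment discontinuation and study withdrawal separately by arm. When treatment is stopped does not change.

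The cost is a protocol amendment with sponsor approval, submitted to the MHRA and REC if judged substantial, plus some extra follow-up at a clinic visit that is already routine. No visits or participants are added.

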11 DATA MANAGEMENT

11.1 Data collection tools and source document identification

Source documents will include the hospital records, drug charts, fluid balance charts, blood test reports and computer record of any blood transfusion. In this study, the CRF will be used as the source document for any correspondence with the patient, height, weight and blood pressure measurements. All study documentation will have the official letterhead of the centre on correspondence. All documents will be stored safely in confidential conditions. On all study-specific documents, other than the signed consent, the participant will be referred to by the study participant number/code, not by name.

11.2 Data handling and record keeping

All study data will be entered onto the CRF and subsequently entered onto a password protected database that will be saved on an NHS computer. A password protected back-up copy of the database will be saved on the Chief Investigator's computer. The participants will be identified by a study specific participants number and/or code in any database. The name and any other identifying detail will NOT be included in any study data electronic file.

11.3 Access to Data

Direct access to data will be granted to authorised representatives from the Sponsor, host institution and the regulatory authorities to permit trial-related monitoring, audits and inspections- in line with participant consent.

11.4 Archiving

As soon as practicably possible after the completion of the study the Sponsor will give permission to the Investigator site to archive their essential documentation. The site will be required to archive their documentation for at 5 years after completion of the study, and no study documentation will be destroyed without prior written agreement between the Sponsor and the Investigator. Should the Investigator wish to assign the study records to another party or move them to another location written agreement must be obtained from the sponsor. Likewise, the sponsor will archive its study documentation for 5 years. All documents will be stored in such a way that they can be accessed at a later date. Consideration will be given to security and environmental risks.

12 MONITORING, AUDIT & INSPECTION

The research sponsor will ensure that arrangements and systems are in place for the management and monitoring of research. The arrangements for monitoring and auditing the conduct of the study will reflect the allocation of responsibilities set out in the Research Governance Framework. As this is a CTIMP, sponsors and investigators will fulfil statutory obligations relating to pharmacovigilance under Part 5 of the Medicines for Human Use (Clinical Trials) Regulations 2004. A Trial Monitoring plan will be developed and agreed by the Sponsor. This will be informed by a Trial Risk Assessment which will consider the safety or physical or mental integrity of the trial participants and the scientific value of the research (including the potential risk associated with the implementation of the intervention and

recruitment which can, if not monitored and mitigated, affect the integrity and smooth running of this trial). This monitoring plan will detail the timing and content of reports to monitor trial conduct and implementation and adherence with the Consolidated Standards of Reporting Trials (CONSORT). This monitoring plan may also include site monitoring.

13 ETHICAL AND REGULATORY CONSIDERATIONS

13.1 Research Ethics Committee (REC) review & reports

The Investigators will ensure that this study is conducted in full conformity with the current revision of the Declaration of Helsinki (last amended October 2000, with additional footnotes added 2002 and 2004). The Investigator will ensure that this study is conducted in full conformity with relevant regulations and with the ICH Guidelines for Good Clinical Practice (CPMP/ICH/135/95) July 1996. The protocol, informed consent form, participant information sheet and any proposed advertising material will be submitted to the HRA, an appropriate Research Ethics Committee (REC), regulatory authorities (MHRA in the UK), and host institution(s) for written approval. The Investigator will submit and, where necessary, obtain approval from the above parties for all substantial amendments to the original approved documents.

13.2 Regulatory Compliance

The trial will not commence until a Clinical Trial Authorisation (CTA) is obtained from the MHRA and Favourable REC opinion. The protocol and trial conduct will comply with the Medicines for Human Use (Clinical Trials) Regulations 2004 and any relevant amendments

Before any site can enrol patients into the study, the Chief Investigator/Principal Investigator or designee will ensure that appropriate approvals from participating organisations are in

place. For any amendment to the study, the Chief Investigator or designee, in agreement with the sponsor will submit information to the appropriate body in order for them to issue approval for the amendment. The Chief Investigator or designee will work with sites (R&D departments at NHS sites as well as the study delivery team) so they can put the necessary arrangements in place to implement the amendment to confirm their support for the study as amended.

13.3 Protocol compliance

Protocol non-compliances will be defined as departures from the approved protocol.

Prospective, planned deviations or waivers to the protocol are not allowed under the UK regulations on Clinical Trials and must not be used e.g. it is not acceptable to enrol a participant if they do not meet the eligibility criteria or restrictions specified in the trial protocol. Accidental protocol deviations will be adequately documented on the relevant protocol deviation form and reported to the Chief Investigator and Sponsor immediately. Deviations from the protocol which are found to frequently recur are not acceptable, will require immediate action and could potentially be classified as a serious breach.

13.4 Notification of Serious Breaches to GCP and/or the protocol

A “serious breach” is a breach which is likely to effect to a significant degree –

- a. the safety or physical or mental integrity of the participants of the trial; or
- b. the scientific value of the trial

In the event of a serious breach the sponsor will be notified immediately of any case where the above definition applies during the trial conduct phase. In addition, the sponsor will notify the licensing authority in writing of any serious breach of

- (a) the conditions and principles of GCP in connection with that trial; or
- (b) the protocol relating to that trial, as amended from time to time, within 7 days of becoming aware of that breach

13.5 Data protection and patient confidentiality

The trial staff will ensure that the participants' anonymity is maintained. The participants will be identified only by initials and a participants ID number on the CRF and any electronic database. All documents will be stored securely and only accessible by trial staff and authorised personnel. The study will comply with the Data Protection Act 2018 which requires data to be anonymised as soon as it is practical to do so.

13.6 Indemnity

This is an NHS-sponsored research study. For NHS sponsored research HSG (96)48 reference no. 2 refers. If there is negligent harm during the clinical trial when the NHS body owes a duty of care to the person harmed, NHS Indemnity covers NHS staff, medical academic staff with honorary contracts, and those conducting the study. NHS Indemnity does not offer no-fault compensation and is unable to agree in advance to pay compensation for non-negligent harm.

